## 1.2 Primary Study Endpoints

Successful completion of data collection of 800 participants (400 players and 400 spokespersons) who play the "Who Would You Choose" game.

## 1.3 Secondary Study Endpoints

Establish feasibility of game intervention

## 2.0 Background

### 2.1 Scientific Background and Gaps

The value of advance care planning (**ACP**, which includes the key task of choosing a spokesperson) has a strong **scientific premise** grounded in decades of randomized controlled trials and public health research. Engaging in ACP: 1) reduces unwanted end-of-life medical interventions; 2) decreases stress; and 3) reduces end-of-life costs by up to 36%. Despite the importance of choosing a healthcare spokesperson, there are surprisingly little data on how to optimize that choice. To our knowledge, no studies examine how best to get people to designate a spokesperson, or how to choose a spokesperson who can/will accurately represents one's wishes. Our own research demonstrates that (for a given clinical scenario) spokespersons do a poorer job representing patients' wishes when patients desire less aggressive care (see *Preliminary Studies*). Moreover, in many states, unless next of kin are formally designated as spokesperson, they (by law) cannot decline life-sustaining treatment unless the patient is permanently unconscious or has an "end-stage condition." Accordingly, to help respect patient autonomy and prevent unwanted end-of-life treatment, interventions are needed that prompt people to designate a spokesperson who can/will accurately represent their wishes when decisions need to be made. Though there is strong professional consensus about the qualities that make for a good spokesperson (is available, has good judgment, knows patient's values, etc.), little is known about which qualities the public considers most important, their rationales for choosing a spokesperson, or the best way to increase concordance between patients' wishes and spokespersons' decisions. A recent systematic review showed that the widely used intervention, Respecting Choices, does increase advance directive completion rates and improve patient–spokesperson concordance, but the model is labor intensive, expensive to implement, and population specific. Less intensive ACP initiatives demonstrate much smaller effect sizes (10% increase in advance directive completion); difficulty getting people to make time for ACP); over-emphasis on static advance directive documents; and problems with implementation. Surprisingly, there is little research on how to help patients choose good spokespersons or prepare them for making treatment decisions. This is important because spokespersons often are unprepared to represent patients' wishes.

What is needed are low-cost, high yield interventions that help people not only designate a spokesperson, but choose the *right* spokesperson. To succeed, such interventions must be appealing and readily scalable. This project will use the novel serious game, *Who Would You Choose: Serious Fun (WWYC)*, to deepen our understanding of how people choose a spokesperson, and move us closer towards a scalable intervention for helping people optimize that choice.

### 2.2 Previous Data

Describe any relevant preliminary data.

We conducted feasibility and pilot testing of a revised WWYC game at 9 different venues with 93 participants (77% female, 25% minorities, see Table 3). Using a 10-point scale, we found that the majority of participants enjoyed playing the game (7.6 +/- 1.6), found it engaging (8.3 +/- 1.6), and would recommend it to others (7.3 +/- 2.3). More importantly, 84% (78/93) of participants reported that playing the game helped them “to think more deeply about the characteristics a healthcare spokesperson should have,” and 75% (70/93) said it prompted them “to think more deeply about who should be their own healthcare spokesperson.”

We refined the game by holding multiple informal game sessions to elicit feedback on game mechanics. Following modifications, we held formal game events using beta-versions of WWYC at 4 different venues (n=39 participants) with games facilitated by research to ensure rigor and fidelity. In post-game focus groups, players reported that playing WWYC was thought-provoking and enjoyable, and that it changed their views about choosing a spokesperson.

Table 3	GAME (Stage 1A)	GAME (Stage 1B)
Participants (n)	39	93
Female	9 (24%)	72 (77%)
Caucasian	18 (46%)	93 (75%)
Events (n)	4	9
Games (n)	8	18

staff

### 2.3 Study Rationale

The serious game WWYC departs from standard ACP practice by transforming the task of “choosing a spokesperson” into a fun, engaging social activity that: 1) is self-contained; 2) does not require extensive training, resource investment, or infrastructure; 3) is readily scalable; and 4) leverages mobile technology (ie, smart-phones) to operationalize one’s choice of a spokesperson and (eventually) assess whether that spokesperson knows one’s wishes for healthcare. WWYC is innovative in that its purpose is not just to get people to choose a spokesperson, but to *improve* that choice –which no other initiative has explicitly attempted.

WWYC is different from typical efforts to designate spokespersons in that it is experiential, not didactic. It employs imaginative and metaphorical questions to help players consider key qualities of ideal spokespersons, to help them realize who in their own life embodies these qualities. This use of playful and thought-provoking questions represents a paradigm-shift for helping people engage in ACP. While other ACP-related games exist, WWYC is unique in its focus on the behavior of choosing a spokesperson, as opposed to prompting general conversations about values, goals, and beliefs.

While most ACP interventions emphasize the somewhat daunting assignment of creating detailed instructions for future medical care, WWYC focuses on a single task: identifying a spokesperson. WWYC will also provide opportunities and structure for meaningful engagement between individuals and their spokespersons. After completing game-play, the WWYC App will prompt players to 1) state which medical treatments they would want in various clinical scenarios, and then 2) send their spokesperson a request (and web link) to predict which medical treatments *they* (the spokesperson) think the player would want in those scenarios. As described in *Future Directions*, the WWYC App will eventually provide notifications to the player/spokesperson dyad about how their answers match up, and send tailored text messages that prompt discussions to help spokespersons be better prepared for their role.

## 3.0 Inclusion and Exclusion Criteria

### 3.1 Inclusion Criteria

Participants must be:

- ≥18 years old
- able to read, write, and speak English
- have a working smart phone
- able and willing to forward post-activity survey to potential spokesperson

Spokesperson must be:

- >18 years old
- able to read, write, and speak English
- have a working smart phone

### **3.2 Exclusion Criteria**

Participants will be excluded, if they are:

- <18 years old
- unable to read, write, and speak English
- not have a working smart phone
- unable or unwilling to forward post-activity survey to potential spokesperson

Spokesperson will be excluded, if they are:

- <18 years old
- unable to read, write, and speak English
- not have a working smart phone

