## **4.0 Recruitment Methods**

### **4.1 Identification of subjects**

To recruit participants, we will advertise via Study Finder, newspaper, radio, fliers posted in local community centers, places of worship, Penn State patient care areas, patient support groups, and word-of mouth of personal contacts, which may also include social media.

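### Prior WWYC play is neither an exclusion nor a listed baseline item, so pre-game answers may already be post-exposure and a near-threshold player rating could be tipped

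*Combined protocol and SAP*

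**What the plan says.** Sections 3.1 and 3.2 give four conditions for players: age, English, a smart phone, and forwarding the survey. The last inclusion item is "able and willing to forward post-activity survey to potential spokesperson" and its mirror in the exclusions is "unable or unwilling to forward post-activity survey to potential spokesperson". The gap shows only when both lists are read in full: neither mentions earlier play of WWYC or a second enrolment.

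Section 2.2 shows that earlier players exist. One stage was "pilot testing of a revised WWYC game at 9 different venues with 93 participants". In another, "we held formal game events using beta-versions of WWYC at 4 different venues (n=39 participants"). There were also informal sessions with no head count: "We refined the game by holding multiple informal game sessions to elicit feedback on game mechanics".

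Recruitment (section 4.1) runs through several public channels and also "word-of mouth of personal contacts, which may also include social media". Section 4.2.4 describes screening without a question on prior play, and keeps names and contact details apart from the Participant ID and the data. The baseline list in section 7.2 (Study Procedures) includes general experience with games, a readiness stage and a pre-activity form on choosing a spokesperson. It lists no item on having played WWYC. Section 8.4 summarises the feasibility outcomes as frequencies and percentages, with no split by earlier exposure.

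**The concern.** Aim 1 asks whether a player's choice of spokesperson changed because of the game. For someone who has played before, the pre-activity form and the readiness stage are not pre-exposure measures. Section 2.2 itself reports that players in the beta-version focus groups said the game altered how they thought about the choice, so an earlier session could already have moved the baseline. This needs no assumed rate and applies to each returning player at any sample size.

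Two of the four Aim 2 criteria, helpfulness and endorsement, are players' own ratings judged against a fixed 75% cut-off without a statistical test. People who choose to come back may like the game more than new players do, and a modest number of them could move a close result across the line. A person who attends two events of this study would also be counted twice.

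The omission is hard to repair afterwards. If prior play is not asked, and contact details are not linked to the data, no listed variable would identify these players.

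**Working it through.** **Inputs.** From section 2.2: 39 and 93 pilot participants, 78/93 and 70/93 favourable on the two items nearest to helpfulness, and a mean of 7.3 (SD 2.3) out of 10 for recommending the game. From section 1.1, Aim 2: 100 players and a 75% cut-off. From sections 1.2 and 8.2: 400 players. The plan has no power calculation to reproduce.

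**Pilot figures.** 78/93 = 83.9% and 70/93 = 75.3%, which match the printed 84% and 75%. The total 39 + 93 = 132 is not printed, and it assumes that the two stages had different people.

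**How many returners would tip a criterion.** Let r be the share of returning players, p_new the favourable rate in new players and p_ret the rate in returners.

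Observed rate = r × p_ret + (1 − r) × p_new. Setting this to 0.75 gives r = (0.75 − p_new)/(p_ret − p_new).

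Take p_new = 0.70 as an assumption, so the numerator is 0.05:

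| p_ret | r | of 100 players | of 400 players | 400-player figure as share of 132 |
|---|---|---|---|---|
| 100% (assumed) | 0.05/0.30 = 0.167 | 17 | 67 | 51% |
| 90% (assumed) | 0.05/0.20 = 0.250 | 25 | 100 | 76% |
| 84% (pilot, as printed) | 0.05/0.14 = 0.357 | 36 | 143 | 108% |

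At the other pilot item's 75.3%, r = 0.05/0.0527 = 0.949, so about 95 of 100 players would have to be returners. At that rate they make almost no difference.

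**Sensitivity to p_new, with fully favourable returners.** From 72%: 0.03/0.28 = 0.107, or 11 of 100 and 43 of 400. From 65%: 0.10/0.35 = 0.286, or 29 of 100 and 115 of 400.

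**A small number of returners.** Ten fully favourable returners lower the rate needed in new players from 75% to (75 − 10)/90 = 72.2% with 100 players, and to (300 − 10)/390 = 74.4% with 400.

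**The extreme case with 400 players.** If all 132 returned and all were favourable, new players would still need (300 − 132)/(400 − 132) = 168/268 = 62.7%. At 84% favourable they would need (300 − 110.9)/268 = 70.6%.

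**The case against.** A reader might infer that the 132 pilot players, being more than the 100 in Aim 2, could carry the helpfulness and endorsement criteria. The documents do not support that, for three reasons.

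- Sections 1.2 and 8.2 give 400 players. At that size even the whole pilot pool, all favourable, leaves new players needing 62.7%.
- Strong favour among returners is an assumption. The pilot's own figures were 84%, 75% and a mean of 7.3 out of 10.
- Nothing says that pilot players or pilot venues will be used again. Recruitment covers newspaper, radio, fliers, patient care areas and support groups across two states, and word of mouth is only one route.

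The pilot also used earlier versions of the game, with answers written by hand (section 7.2), so the earlier exposure was not identical to the present one. The questionnaires are not in the documents, so one of them may ask about prior play, and it may come up in the two-week interviews. Finally, this is a single-arm feasibility study with descriptive summaries, and two of the four Aim 2 criteria are not ratings.

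Most of this limits the size of the point and should be accepted. It does not close the gap. Nothing in the listed criteria, screening or baseline items stops or records a return, including a second attendance within this study over a recruitment period from August 2021 to June 2023, with a gift card of $50 offered to players. An interview remark is not a variable by which the percentages can be split. An earlier version that changed players' views is enough to compromise a pre-activity answer.

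**Conclusion.** The point holds in a limited form. As written, people who have already played WWYC may enrol and no listed item records it. For any such player the pre-game choice and readiness data are post-exposure, which bears directly on Aim 1. How many there would be is unknown.

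The effect on the Aim 2 ratings is conditional. Returners could tip a result already near 75%; they could not rescue a clearly poor one at 400 players. The size rests on two assumptions, the rate in new players and the rate in returners. It also depends on the number of players, which the plan gives as both 100 and 400. In-study repeat play could enlarge the pool beyond 132 by a number that the documents do not allow one to estimate. The case for acting is that the remedy is cheap now and probably unavailable once data are collected.

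**What to change.** 1. Add to the player exclusions in section 3.2: *has previously played any version of WWYC, including pilot or informal sessions or an earlier event in this study*.
2. Ask about it in the screening conversation described in section 4.2.4.
3. Add a prior-play item to the baseline form in section 7.2 (Study Procedures). The screening question alone is not enough, because contact details are kept apart from the data. The baseline item stays with the player's other answers and catches anyone whom screening misses.
4. State in section 8.4 that the pre-game choice and readiness data, and the two player-rated Aim 2 percentages, are reported in first-time players.

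If the sponsor prefers not to exclude prior players, items 3 and 4 are the minimum. The cost is one exclusion line, one screening question, one baseline item and a sentence in the analysis section, together with the loss of a few easy recruits.

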### **3.3 Early Withdrawal of Subjects**

#### **3.3.1 Criteria for removal from study**

n/a

#### **3.3.2 Follow-up for withdrawn subjects**

n/a

## **4.0 Recruitment Methods**

### **4.1 Identification of subjects**

To recruit participants, we will advertise via Study Finder, newspaper, radio, fliers posted in local community centers, places of worship, Penn State patient care areas, patient support groups, and word-of mouth of personal contacts, which may also include social media.

### **4.2 Recruitment process**

#### **4.2.1 How potential subjects will be recruited.**

To recruit participants, we will advertise via Study Finder, newspaper, radio, fliers posted in local community centers, places of worship, Penn State patient care areas, patient support groups, and word-of mouth of personal contacts, which may also include social media.

#### **4.2.2 Where potential subjects will be recruited.**

Participants will be recruited throughout Pennsylvania and New Jersey regions.

#### **4.2.3 When potential subjects will be recruited.**

August 2021 to June 2023

#### **4.2.4 Describe the eligibility screening process and indicate whether the screening process will occur before or after obtaining informed consent. Screening begins when the investigator obtains information about or from a prospective participant in order to determine their**

**eligibility. In some studies, these procedures may not take place unless HIPAA Authorization is obtained OR a waiver of HIPAA Authorization when applicable for the screening procedures is approved by the IRB.**

Interested participants will be informed about the study and screened for eligibility during that initial conversation (in person, via telephone, email or Zoom). Names, phone numbers, or emails will only be used for screening or scheduling purposes and will not be linked to Participant ID or data.

## 5.0 Consent Process and Documentation

### 5.1 Consent Process:

Check all applicable boxes below:

- Informed consent will be sought and documented with a written consent form *[Complete Sections 5.2 and 5.6]*
- Implied or verbal consent will be obtained – subjects will not sign a consent form (waiver of written documentation of consent) *[Complete Sections 5.2, 5.3 and 5.6]*
- Informed consent will be sought but some of the elements of informed consent will be omitted or altered (e.g., deception). *[Complete section 5.2, 5.4 and 5.6]*
- Informed consent will not be obtained – request to completely waive the informed consent requirement. *[Complete Section 5.5]*

The following checkbox is for all locations EXCEPT Penn State Health and College of Medicine:

**Exempt Research at all Locations Except Penn State Health and the College of Medicine:** If you believe that the research activities outlined meet one or more of the criteria outlined in “HRP-312-Worksheet- Exemption Determination.” Please verify by checking this box that if conducting an exempt research study, the consent process will disclose the following (all of which are included in “HRP-590- Consent Guidance for Exempt Research”):

Penn State affiliation; name and contact information for the researcher and advisor (if the researcher is a student); the activities involve research; the procedures to be performed; participation is voluntary; that there are adequate provisions to maintain the privacy interests of subjects and the confidentiality of the data; and subjects may choose not to answer specific questions.

**If the research includes the use of student educational records include the following language in this section (otherwise delete):** The parent or eligible student will provide a signed and dated written consent that discloses: the records that may be disclosed; the purpose of the disclosure; the party or class of parties to whom the disclosure may be made; if a parent or adult student requests, the school will provide him or her with a copy of the records disclosed; if the parent of a student who is not an adult so requests, the school will provide the student with a copy of the records disclosed.

**Note: If this box has been checked, skip the remainder of section 5 and proceed to section 6 of this protocol. If the investigator’s assessment is inaccurate, an IRB Analyst will request revision to the protocol and that an informed consent form be submitted for review and approval. Except for exemptions where Limited IRB Review (see “HRP-312- Worksheet- Exemption Determination”) is required or where otherwise requested by the IRB, informed consent forms for research activities**

**determined to be exempt without Limited IRB Review are generally not required to be submitted for review and approval by the University Park IRB.**

## 5.2 Obtaining Informed Consent

### 5.2.1 Timing and Location of Consent

Players:

Consent will be obtained at the time of the single study visit which will take place at Penn State Hershey Medical Center and public locations within the community.

Spokespersons:

Consent will be obtained within REDCap ahead of survey questions.

### 5.2.2 Coercion or Undue Influence during Consent

- Subjects will be notified in writing (see Summary Explanation of Research) that participation in this research is strictly voluntary.
- If the subject does not agree to participate, they will not be included in the study activities.
- Participants will be given as much time as needed to ask and have questions answered about the study and their decision whether to participate.

## 5.3 Waiver of Written Documentation of Consent

### 5.3.1 Indicate which of the following conditions applies to this research:

- The research presents no more than minimal risk of harm to subjects and involves no procedures for which written consent is normally required outside of the research context.

OR

- The only record linking the subject and the research would be the consent document and the principal risk would be potential harm resulting from a breach of confidentiality. Each subject will be asked whether the subject wants documentation linking the subject with the research, and the subject's wishes will govern. *(Note: This condition is not applicable for FDA-regulated research. If this category is chosen, include copies of a consent form and /or parental permission form for participants who want written documentation linking them to the research.)*

OR

- If the subjects or legally authorized representatives are members of a distinct cultural group or community in which signing forms is not the norm, that the research presents no more than minimal risk of harm to subjects and provided there is an appropriate alternative mechanism for documenting that informed consent was obtained. *(Note: This condition is not applicable for FDA-regulated research.)*

Describe the alternative mechanism for documenting that informed consent was obtained:

### 5.3.2 Indicate what materials, if any, will be used to inform potential subjects about the research (e.g., a letter accompanying a questionnaire, verbal script, implied consent form, or summary explanation of the research)

Players:

A Summary Explanation of Research will be provided prior to the start of study activities.

Spokespersons:

A Summary Explanation of Research will be provided within REDCap prior to the start of survey questions.

**5.4 Informed consent will be sought but some of the elements of informed consent will be omitted or altered (e.g., deception).**

**5.4.21 Indicate the elements of informed consent to be omitted or altered**

Not applicable.

**5.4.22 Indicate why the research could not practicably be carried out without the omission or alteration of consent elements**

Not applicable.

**5.4.23 Describe why the research involves no more than minimal risk to subjects.**

Not applicable.

**5.4.24 Describe why the alteration/omission will not adversely affect the rights and welfare of subjects.**

Not applicable.

**5.4.25 If the research involves using identifiable private information or identifiable biospecimens, describe why the research could not be practicably be carried out without using such information or biospecimens in an identifiable format.**

Not applicable.

